Study Objective

To assess the efficacy of povidone-iodine wash before wound closure in preventing surgical site infections.

Trial Design

Superiority, parallel group randomized controlled trial, allocation 1:1

Methods

Study Setting

Operative theatres at Ain Shams University Hospitals

Inclusion Criteria

- Adult patients (≥ 18 years old)
- Open and minimally invasive surgeries
- Emergency (any unplanned admission) and elective (planned admission) surgical procedures
- Clean, Clean-Contaminated, Contaminated, Dirty wounds [22], (See appendix 1)
- Inclusion surgery list according to Current Procedural Terminology (CPT) National Healthcare Safety Network (NHSN) operative procedure code mapping [23] , List of included surgical procedures (See appendix 2)

Exclusion Criteria

- Povidone-iodine allergy
- Surgeries for infected wounds.
- Exclusion surgery list according to Current Procedural Terminology (CPT) National Healthcare Safety Network (NHSN) operative procedure code mapping, [23] List of excluded surgical procedures, (See appendix 3)

Intervention

- 10% povidone iodine wound wash before wound closure versus direct wound closure.
- Antibiotic prophylaxis will be administered according to local protocols.
- Wound dressing type and frequency will not differ between both groups.
- Diagnosed SSIs will be managed according to local antibiograms and management guidelines.

Outcomes

- Primary: Incidence of superficial and deep surgical site infection (SSI) within 30 days postoperatively
- Secondary:
 1. Post-operative morbidity and mortality by (Clavien-Dindo classification system) [24], (See appendix 4)
 2. Length of hospital stay
 3. Readmission and Reoperations related to surgical site infection
 4. Infectious complications (Sepsis, septic shock, multiple-organ dysfunction syndrome, wound dehiscence) [25-28]
 5. Microbiology culture and sensitivity results
 6. Local adverse events for povidone-iodine application (Local irritation, poor wound healing)
 7. Cost-analysis

Participant Timeline

Recruitment will start from day (18/09/2021) till sample size is reached.

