Patients will be introduced to and asked to participate in the trial when they arrive to the surgical ward or emergency department by the surgical resident. They will not be subjected to any additional steps other than the standard hospital protocols as our trial begins in the operating room where patients will be randomly allocated into 2 groups: the control group (direct wound closure) and the intervention group (PVI wound wash before closure).

After the operation, patients will be monitored and observed at the hospital by the staff until discharge and will be given a specialized follow-up card. Following discharge, follow-up will be in the form of fixed outpatient clinic visit after the first week postoperatively and continue with phone calls made at regular 1-week intervals inquiring about symptoms and signs of SSI based on a questionnaire guided by the CDC definitions [27]. If a patient displays ≥ 1 symptom listed in the CDC checklist (See appendix 5), he/she will be invited to follow-up in our outpatient clinic and will be identified by their card. This will allow the physician to fill out the data collection form in their files and obtain a picture for documentation purposes. Follow-up will continue for a period of 30 days.

Sample Size

Using PASSII program for sample size calculation and assuming SSI incidence of 10% in control group and 5% in intervention group, setting **power** at 80% and **α -error** at 0.05, sample size of 345 patient for each group will be needed. We plan to enroll an additional 10% of the calculated sample size for each group in anticipation of a loss to follow-up rate of 10%. The total sample size will be **760 patients**.

Assignment of Interventions

Sequence Generation

A statistician not directly involved in the study or analysis will prepare a computer-generated randomization sequence. No blocking will be used. The sequence will be provided to the trialists in the form of serially numbered opaque envelopes containing details of either the intervention or the control and a random identifier.

Enrolment and Allocation Concealment

The patients will be enrolled by the resident doctors and given a study ID number.

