The study participants will be divided into 4 groups (Clean, Clean-contaminate, Contaminated, Dirty).

Each group will be stratified and analyzed separately.

Subgroup analyses will also be performed according to the type of surgical access (open versus minimally invasive), and the presence or absence of Diabetes.

The need for additional subgroup analyses will be determined at the time of completion of data collection.

Both per-protocol and intention to treat analyses will be used and their findings will be reported.

Monitoring

The study will not employ a data monitoring committee (DMC) as the trial is conducted on an adult population with no perceived risk to either arm of the trial.

Interim analysis will be done on reaching 50% of the total sample size by an independent statistician blinded for the intervention allocation. The unblinded data will be reported to the Ain Shams Surgical Research Group. The primary purpose of this analysis would be to determine if the study should be prematurely terminated in the case of patient harm. The final decision on the matter will reside with the Ain Shams Surgical Research Group and the study's principal investigators.

In our study an adverse event will be defined as any medical occurrence in a subject with a probable causal relation to the intervention.

Adverse events will be collected after the subject has provided consent and enrolled in the study.

The known as well as novel adverse effects of the study intervention (povidone iodine) will be investigated and recorded until the period of patient follow up is completed.

Ethics and Dissemination

Ethical Approval

This protocol, the template informed consent forms (Arabic and English versions), and any subsequent modifications will be reviewed and approved by the applicable IRB [institutional review board] with respect to scientific content and compliance with applicable research and human subjects' regulations prior to starting the study.

Protocol Amendments

Any modifications to the protocol which may impact on the conduct of the study, potential benefit of the patient or may affect patient safety, including changes of study objectives, study design, patient population, sample sizes, study procedures, or significant administrative aspects will require a formal amendment to the protocol. Such amendments will be reviewed and approved by the IRB prior to implementation in accordance with local regulations.

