Class I/Clean: An uninfected operative wound in which no inflammation is encountered, and the respiratory, alimentary, genital, or uninfected urinary tract is not entered. In addition, clean wounds are primarily closed and, if necessary, drained with closed drainage. Operative incisional wounds that follow no penetrating (blunt) trauma should be included in this category if they meet the criteria.

[figure not shown]
Class II/Clean-Contaminated: An operative wound in which the respiratory, alimentary, genital, or urinary tracts are entered under controlled conditions and without unusual contamination. Specifically, operations involving the biliary tract, appendix, vagina, and oropharynx are included in this category, provided no evidence of infection or major break in a sterile technique is encountered.

Class III/Contaminated: Open, fresh, accidental wounds. In addition, operations with major breaks in a sterile technique (eg, open cardiac massage) or gross spillage from the gastrointestinal tract, and incisions in which acute or no purulent inflammation is encountered are included in this category.

Class IV/Dirty-Infected: Old traumatic wounds with retained devitalized tissue and those that involve existing clinical infection or perforated viscera. This definition suggests that the organisms causing postoperative infection were present in the operative field before the operation.

CDC = Centers for Disease Control and Prevention.

Algorithm for wound classification

(2) Included surgeries

1. Vascular surgeries

- a) **Abdominal aortic aneurysm repair** (Resection of abdominal aorta with anastomosis or replacement)
- b) **Limb amputation** (Total or partial amputation or disarticulation of the upper or lower limbs, including digits)
- c) **Shunt for dialysis**
- d) **Carotid endarterectomy** (Thromboendarterectomy, including patch graft, Reoperation, carotid, thromboendarterectomy, more than 1 month after original operation)

2. Hepatobiliary surgeries

- a) **Bile duct, liver, and pancreatic surgery** (Excision of bile ducts or operative procedures on the biliary tract, liver, or pancreas)
- b) **Gallbladder surgery** (Cholecystectomy and cholecystostomy)
- c) **Liver transplant**

3. Gastrointestinal surgeries

- a) **Appendectomy**
- b) **Intestinal resection and anastomosis**
- c) **Segmental colectomies** (Incision, resection, or anastomosis of the large intestine; includes large-to-small and small-to-large bowel anastomosis)

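### Wound class serves only to split the sample into four separate analyses; one overall comparison stratified by class would be modestly more precise at almost no cost

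*Protocol*

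**What the plan says.** Trial Design describes the study as "Superiority, parallel group randomized controlled trial, allocation 1:1". Sequence Generation provides for one computer-generated sequence, names no stratification factor and adds "No blocking will be used". Under Enrolment and Allocation Concealment, the envelope is opened directly before wound closure.

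All four wound classes are eligible. Statistical Methods divides the participants into those classes and continues "Each group will be stratified and analyzed separately". No pooled estimate that takes class into account is described, and the test itself is left open.

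The Sample Size section is built on one overall comparison: "assuming SSI incidence of 10% in control group and 5% in intervention group", and then "setting power at 80% and α -error at 0.05, sample size of 345 patient for each group will be needed". With the allowance for loss to follow-up, "The total sample size will be 760 patients".

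Appendix 1 describes Class IV wounds as ones where "the organisms causing postoperative infection were present in the operative field before the operation". The operative form in Appendix 6 has a box for each wound class. The same form carries the patient's random code.

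**The concern.** Appendix 1 implies that baseline infection risk differs between wound classes, and Statistical Methods makes class the first grouping of the data. When a baseline factor predicts the outcome, an overall comparison that ignores it has a larger standard error than it needs. A chance difference in case mix between the arms then stays in the estimate.

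The one use of wound class that the protocol states does not address this. Analysing each class on its own produces four small comparisons, none of them planned for in the sample size, and leaves the overall comparison as it was. At stake is some power for the primary outcome, in a trial planned around a difference of 5 percentage points.

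**Working it through.** **1. The plan's own figure.** Inputs from Sample Size: p0 = 0.10, p1 = 0.05, power 80%, alpha 0.05, sidedness not stated. With p̄ = 0.075,

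n per group = [z_α √(2p̄(1−p̄)) + z_β √(p0(1−p0) + p1(1−p1))]² / (p0−p1)²

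- One-sided: (1.645 × 0.3725 + 0.842 × 0.3708)² / 0.0025 gives 343, which reproduces the stated 345 closely.
- Two-sided: the same formula with 1.960 gives 435.
- 345 × 1.10 = 379.5, rounded up to 380 per group, gives 760.

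With 345 per group and a two-sided 5% test, the power by formula is 70.4%. The sidedness question is a separate and larger matter. It is mentioned only because it explains the starting power below.

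**2. Size of the chance imbalance.** Under simple 1:1 allocation of N = 690 evaluable patients, the difference between arms in mean baseline risk has

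SD = 2 √(V_b / N),

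where V_b is the between-class variance of risk averaged over the two arms. The protocol gives no class mix and no class risks, so assumed values are needed. Take a mix of 40/35/15/10% (clean to dirty) with control risks 4/8/16/32%, halved by treatment:

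- Arm-averaged risks are 3/6/12/24%, with mean 7.5%.
- V_b = 0.40(0.045²) + 0.35(0.015²) + 0.15(0.045²) + 0.10(0.165²) = 0.00392.
- SD = 2 √(0.00392/690) = 0.48 percentage points.
- The share of outcome variance explained by class is 0.00392 / (0.075 × 0.925) = 5.6%, roughly what stratification can recover.

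**3. Gain from a stratified overall analysis.** For each scenario, 60,000 trials were simulated with 690 evaluable patients, simple allocation, 10% overall control risk, risk halved in every class and a two-sided 5% test. The unadjusted test of proportions is compared with the Cochran-Mantel-Haenszel (CMH) test over the four classes.

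| Assumed mix (%), clean to dirty | Assumed control risks (%) | SD of chance risk difference (points) | Variance reduction | Power, unadjusted to CMH | Worth about (patients) |
|---|---|---|---|---|---|
| 40/35/15/10 | 7/9/14/18* | 0.21 | 1% | 71.3% to 71.4% | 5 |
| 25/25/25/25 | 3/6/11/20 | 0.37 | 3% | 71.1% to 72.5% | 20 |
| 40/35/15/10 | 4/8/16/32 | 0.48 | 5% | 71.2% to 73.4% | 37 |
| 50/25/10/15 | 2/6/15/40 | 0.75 | 14% | 71.1% to 77.2% | 117 |

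*Scaled slightly upward so that the overall control risk is 10%.

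With no treatment effect, rejection rates stayed near 5% for both tests. A second set of assumptions (mix 35/40/15/10%, a common odds ratio that halves the overall risk) gave variance reductions of 0.8%, 3.4% and 8.6% for control risks of 6/10/14/18%, 4/9/17/25% and 2/7/20/35%. All lie within the range above.

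**4. What separate analyses deliver.** For a halved risk, power within a single class ran from 10% (86 per arm, 3% versus 1.5%) to 61% (about 52 per arm, 40% versus 20%). It was below 50% in all but one of the 16 assumed classes.

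**5. What changing the allocation would add.** Balancing the arms within class, on top of the stratified analysis, added between nothing and 0.7 points of power. Almost all of the gain comes from the analysis.

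**The case against.** The strongest objection is that the choice of test and any adjustment are normally settled in the SAP. None is at hand here, and the protocol does not forbid adjustment. That stands as far as it goes: a reader might infer that the overall comparison is fixed as unadjusted, or that there will be none, and the text says neither. But the protocol is not merely silent. It names a use for wound class, and the use it names recovers none of the available precision.

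A reader might also infer that unblocked allocation is itself a flaw that calls for stratified envelopes. The documents do not support this. Simple randomisation is unbiased and keeps the type I error. Leaving out blocks also helps protect concealment where surgeons cannot be fully blinded. Uneven splits within a class sound worse than they are: a class of 76 patients has an 8.5% chance of a 60:40 split or worse, but at 60:40 the relative efficiency is 4 × 0.6 × 0.4 = 0.96, a 4% loss in that class alone.

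Other parts of the objection also stand:

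- No section calls wound class the main determinant of infection. That its risk gradient is material is an inference from Appendix 1 and from the grouping in Statistical Methods.
- Steep gradients are the less secure assumption, because surgery for infected wounds is excluded and that removes part of the dirty class.
- Adjusting for every recorded predictor would not be free. The planned rates imply 345 × 0.10 + 345 × 0.05 = 51.75, or about 52 events. A model with treatment (1), wound class (3), emergency status (1), diabetes (1), ASA (4), BMI (1) and age (1) has 12 parameters, about 4 events for each.
- Age in bands can enter a model as recorded, so the form needs no change on that account.

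**Conclusion.** The point holds as a modest, nearly free improvement in precision. The only analytic use of wound class that the protocol states produces four underpowered comparisons and does not help the overall one. A pooled comparison stratified by class would lower the variance by about 1% to 14%, worth 0 to 6 points of power, with type I error unchanged.

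The size rests wholly on assumed class mixes and class risks. With a shallow gradient the gain is negligible; the upper end needs something like 40% infection in dirty wounds. The power figures also assume 690 evaluable patients and a two-sided test. This is not a finding of bias, of an invalid design or of faulty randomisation.

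**What to change.** In Statistical Methods, state that the primary comparison of the arms is one pooled analysis stratified by wound class, for example a CMH test with a Mantel-Haenszel risk difference and its confidence interval. Report the four class-specific results as subgroup analyses. With 1:1 allocation the Mantel-Haenszel weights are nearly proportional to class size, so the quantity estimated remains essentially the overall risk difference.

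Require wound class to be recorded before the envelope is opened. The operative form also holds the random code, which is noted after the wash or direct closure. Fixing the order ensures that class is a true baseline factor, assigned without knowledge of the arm.

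Limit any further adjustment to one or two covariates that are already recorded and are named in advance, such as emergency or elective status and diabetes. Statistical Methods leaves additional subgroup analyses to be decided once data collection is complete, and a covariate chosen at that stage would be open to challenge.

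The cost is a few sentences in the protocol and one instruction on the order of recording. It needs no extra patients and no change to the envelopes.

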The allocation sequence will be made available to the OR head nurse in the form of sealed envelopes. The head nurse will provide the surgeons with closed opaque envelopes which will be opened by the nurse directly before wound closure. The head nurse will ensure that the envelopes are opened at wound closure and not before it. After the intervention/control is carried out, the random identifier will be noted down in the patient's operative data collection form. Following that, the nurse will tear the envelope and its contents.

Blinding

The patients and outcome assessors will be blinded. The details of which intervention was used will not be recorded in the regular patient records. The surgeons will be blinded till directly before wound closure, however, because of the nature of intervention, complete blinding of the surgeons would be impossible.

Data Collection Methods

Preoperative data collection will aim to collect baseline data about the recruited patients: patient identifiers, age, BMI, comorbidities including hypertension, diabetes, CKD, chronic liver disease, chronic heart failure, as well as any documented medication use and ASA score; through a standardized data collection form. All patients will be monitored by the doctors who will be responsible for filling their follow-up data till 30 days postoperatively (See appendix 6 for data collection forms).

Teams of four (surgeons or medical students) will be recruited to collect data from included surgical departments, each team collecting information over a two-week interval from all patients undergoing included surgical procedures in the department. Teams will then follow up with patients recruited in this allowed interval over the 30-day follow-up period, according to the methods described above.

We will obtain written informed consent from participants before surgery explaining the study procedures and the follow-up plans. All those who volunteer will be followed up in our clinics and provided carefree-of-cost.

Data Management

Package: R (latest available version)

Methods: Descriptive statistics will be presented as mean \pm SD for quantitative data. If the data is severely skewed/not normally distributed, median and IQR will be used. N & percentile will be used for qualitative data. Relevant statistical tests will be reported when applicable.

Statistical Methods

Suitable statistical tests will be used for data analysis.

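### The patient is tied to an allocation only after treatment and the card is then destroyed, so the assigned and delivered arms cannot be fully verified for the ITT and per-protocol analyses

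*Protocol*

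**What the plan says.** Under Sequence Generation, "A statistician not directly involved in the study or analysis will prepare a computer-generated randomization sequence". It reaches the theatre as "serially numbered opaque envelopes containing details of either the intervention or the control and a random identifier". Residents enrol the patient and give a study ID before any envelope is opened.

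Under Enrolment and Allocation Concealment, the head nurse supplies the envelope, "which will be opened by the nurse directly before wound closure". Then: "After the intervention/control is carried out, the random identifier will be noted down in the patient's operative data collection form". Then: "Following that, the nurse will tear the envelope and its contents".

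Under Blinding, "The details of which intervention was used will not be recorded in the regular patient records". The same section accepts that the surgeon cannot be kept blind once closure begins.

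The operative sheet in Appendix 6 carries the study ID and one blank for the random code. It has no field for the envelope's serial number, the arm assigned or the arm delivered.

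Under Statistical Methods, "Both per-protocol and intention to treat analyses will be used and their findings will be reported".

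**The concern.** An intention-to-treat analysis needs a fixed moment of randomisation and a record of the assigned arm that does not depend on what happens next. Here the nurse opens the card, the surgeon learns the arm, and only after the procedure is anything written that ties this patient to this card. The paper evidence is then destroyed.

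Three things are at stake:

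- Patients whose allocation was not followed are the ones intention-to-treat exists to keep, and they are the most likely to be left without a code.
- One handwritten code becomes the sole link between patient and arm, with nothing to check it against.
- A per-protocol analysis needs to know who received what, and no record of delivered treatment is described.

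Any loss would occur after the operator knows the arm, so it need not be random.

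**Working it through.** No figure in the protocol is disputed on this point. The check is to trace the records, and then to see how much simple miscoding could matter.

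**1. What is written, and when**

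- Enrolment: study ID. No arm exists yet.
- Opening of the envelope: arm revealed. No entry is specified.
- Wash or direct closure: no entry is specified.
- Afterwards: random code written on the operative form, beside the study ID.
- Then: envelope and card destroyed.
- Analysis: code on the form plus the statistician's key gives the arm assigned. Nothing gives the arm delivered.

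**2. What that chain can and cannot resolve**

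| Event | Can it be noticed? | Can it be resolved? |
|---|---|---|
| Envelope opened, allocation not carried out, no code written | Yes, if someone compares forms with the sequence: a study ID without a code, and an unused code | Not reliably once several patients lack codes, because envelope number and time are not recorded |
| Code blank or illegible | Yes | Not from source |
| Code mis-copied to an invalid or duplicate value | Yes, against the sequence | Not from source |
| Two valid codes exchanged between patients | No | No |
| One envelope passed over and another opened | Possibly, as an unused code | No: nothing shows for whom it was opened, or why |
| Wash given under a control card, or omitted under a wash card | No: there is no delivered-arm field | No |

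The protocol describes no reconciliation, so even the entries marked as noticeable depend on an unplanned step.

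**3. Arm totals are no substitute check**

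No blocking is used. With simple 1:1 allocation of 760 patients, chance alone moves one arm's total by about ±1.96 × √(760 × 0.5 × 0.5) = ±1.96 × 13.8 = ±27. A handful of discarded envelopes would be invisible in that.

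**4. Random miscoding**

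Inputs from Sample Size: 10% against 5%, 345 per group, 80% power, α 0.05. The usual pooled formula gives 343 per group one-sided and 435 two-sided, so 345 fits a one-sided test. Sidedness is not stated; that is a separate matter, and power is shown both ways. The total is 345 × 1.10 = 379.5, rounded to 380, × 2 = 760.

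If a share m of each arm is coded to the other, the observed difference is 5 × (1 − 2m) points. The values of m are assumptions.

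| m | Difference (points) | Power at 345 per arm, one-sided | Two-sided |
|---|---|---|---|
| 0 | 5.0 | 80.3% | 70.4% |
| 1% | 4.9 | 78.9% | 68.6% |
| 2% | 4.8 | 77.4% | 66.8% |
| 5% | 4.5 | 72.6% | 61.2% |

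At m = 2.5% the difference is 5 × 0.95 = 4.75 points. In patients, 1–2.5% of 760 is about 8 to 19. This dilution is small.

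**5. Selective loss (illustration only)**

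Suppose the wash has no effect, the infection risk is 10%, and a share f of the wash arm with risk r goes missing. The observed wash-arm risk is (0.10 − f·r)/(1 − f).

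- f = 1%, r = 20%: 0.098/0.99 = 9.9%.
- f = 5%, r = 40%: 0.080/0.95 = 8.4%.

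With 345 per arm before loss, the chance that a two-sided 5% test wrongly favours the wash goes from 2.5% to 2.8% and 10.1% respectively. The documents supply neither f nor r, and the direction reverses if the loss is in the control arm. The illustration shows why selective loss matters more than random miscoding. It does not show that such loss will occur.

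**The case against.** The other side has real weight, and it rules out several stronger readings.

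- A reader might infer that the torn card was the only source of the allocation. It was a copy. The forms carry only a code, so analysis by arm presupposes that the statistician's sequence survives as the key. It follows that for a correctly recorded patient the arm can still be found, including after a suspected reaction.
- A reader might infer that coding errors or skipped envelopes leave no trace. Blank, invalid, duplicate or unused codes would all show against the sequence, and the study ID identifies the patient who lacks a code. Only an exchange of two valid codes, or treatment contrary to the card, is truly invisible.
- A reader might infer that patients whose allocation was not executed are excluded by rule. The text fixes a time for writing the code; it does not state an exclusion. The gap between opening and recording is short, a wash patient who is not washed is simply closed, and the form still has its blank.
- Tearing the card protects the blinding of patients and assessors, since doctors and students handle the forms.
- Logs and storage could sit in a theatre procedure outside the protocol.

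The first three points stand, and the concern is worded to respect them. The last two do not remove it. Sealed storage protects blinding equally well and keeps the evidence. The tear-up step is something the protocol itself fixes, so a separate procedure would have to contradict it, and a statistical analysis plan cannot restore a destroyed source. The logbooks mentioned under Healthcare-Information Security and Privacy link study numbers to personal identity, not to allocations.

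**Conclusion.** The concern holds as one of auditability and intention-to-treat integrity, not as a demonstrated error in the result. As written, a patient may be left without a recorded arm after the envelope has been opened. A faulty code may be seen but not corrected from source, an exchange of valid codes cannot be seen, and the per-protocol set cannot be built from any described record of treatment delivered.

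No size follows from the documents. Random miscoding at an assumed 1–2.5% costs 0.1 to 0.25 of the planned 5 points, which would not threaten the trial. The case for change rests on loss that cannot be verified and that could be selective, because it would arise after the surgeon knows the arm. The harm is irreversible for each patient once the card is torn, while prevention costs almost nothing. This is a worthwhile, cheap improvement to make before recruitment starts.

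**What to change.** Amend Enrolment and Allocation Concealment and the operative sheet in Appendix 6:

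1. At opening and before closure, the nurse enters the study ID, envelope serial number, random identifier and time in a theatre log. The log need not show the arm. State that the patient counts as randomised from that entry, whatever is then done.
2. Copy the serial number and the random identifier to the operative form.
3. Record the arm actually delivered on a separate study sheet withheld from outcome assessors. This leaves the routine notes free of the treatment, as Blinding intends.
4. Replace the tear-up step with sealed, opaque storage of the opened envelope and card, away from data collectors and assessors.
5. Reconcile log and envelopes with the statistician's master sequence at the halfway interim and at the final analysis.

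The cost is a short amendment, a log sheet, an extra one-line form and opaque bags, with a little more paperwork in theatre. The one downside is a small risk to blinding if stored cards are handled carelessly, which storage apart from the data teams should contain.
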